#### 7.1.2. Identification and recruitment of informal carers

In cases in which PWD seeking healthcare are accompanied by an informal carer, the carer will be aware of the study from the outset. The informal carer will receive an informal carer PIS by the clinical researcher at the earliest opportunity. In most cases, this will be when the follow-up call occurs to seek verbal consent from the PWD to contact their GP practice to confirm eligibility. It is probable that the informal carer will answer the telephone, instead of the PWD. If the PWD is not accompanied by an informal carer, we will ask the PWD to identify whether they have an informal carer who helps with day to day activities and who might be interested in being involved in the study. If the PWD can provide a name and address, the clinical researcher will send the informal carer and invitation letter and PIS. If the PWD provides a name and phone number, the informal carer will be contacted for an address. If

Page 31 of 59

the PWD can only provide a name, the clinical researcher will send the invitation letter and PIS addressed to the informal carer, c/o the PWD to the PWD's address.

#### 7.1.3. Identification and recruitment of professionals

The process evaluation will examine implementation, acceptability of the intervention for participants and practitioners, mechanisms of impact, and context. The process evaluation will be structured using a logic model, representing an initial theory of how the intervention works and will be revised according to study findings. The datasets for the process evaluation are: 18 paired interviews with people with dementia and their carers; 24 interviews with practitioners delivering the intervention; six interviews with study research nurses; observations of six intervention sessions; observations of four supervision sessions; and observations of four multidisciplinary team (MDT) meetings. Trial records of fidelity, dose, reach and attrition will also be collected to inform the process evaluation and to assess the feasibility of the study processes.

#### 7.1.3.1. Participant sampling, recruitment and consent

Recruitment and consent for people with dementia aged over 50 years old and their carers (referred to here as 'participants') in the process evaluation will be included in the consent process for the overall study. Information about the process evaluation will be included in the Participant Information Sheet, and participant consent forms will include an optional section for consent to (1) a face-to-face, paired interview with a qualitative researcher (2) one or more intervention sessions to be observed by a qualitative researcher. Consent forms will include an item explaining that participants can withdraw their qualitative data from the study up to the point at which analysis is conducted, giving an approximate date for this.

Patient-carer pairs will be sampled for maximum variation (such as gender, site) by the study qualitative researcher, drawing on trial records. The researcher will then contact participants by email or telephone to invite them to take part in an interview, which will be conducted around the end of the intervention to avoid Hawthorne effects. A total of 18 interviews will be conducted. Consent will be reconfirmed verbally at the beginning of the interview.

#### 7.1.3.2. Practitioner sampling, recruitment and consent

One or two clinical research nurses will be located at each of the six sites. The study qualitative researcher will liaise with the clinical research nurses to identify intervention practitioners from the six sites to invite for interview and to take part in MDT meeting observations, supervision observations and intervention session observations. Interviews will include geriatricians, physiotherapists, occupational therapists and support workers. Only geriatricians who are not co-applicants (i.e., not members of the research team) will be invited to interview. Approximately four practitioners from each site will be interviewed, with a total of 24 practitioner interviews conducted overall. The clinical research nurse will invite practitioners verbally or by email, and will provide practitioners with a participant information sheet and consent form at this stage. Contact details of practitioners agreeing to take part will be sent by the research nurse to the study qualitative researcher who will then contact the practitioner to arrange the return of the consent form and a time to conduct the interview or observe a session. Practitioners will have an opportunity to consent to an interview, session observation, supervision observation, MDT meeting observation, or all four.

Page 32 of 59

A clinical research nurse from each of the six sites will be invited by the study qualitative researcher to take part in an interview about the research processes (e.g., participant recruitment). An invitation, participant information sheet and consent form will be emailed to the research nurse, after which the study qualitative researcher will contact the research nurse to arrange the interview.

Consent forms will be sent out and returned to the study qualitative research electronically where possible. Paper copies with an SAE will be sent to potential interviewees where requested. All consent forms will include an item explaining that interviewees can withdraw their qualitative data up to the point at which analysis is conducted, giving an approximate date for this. Consent will be re-confirmed verbally at the beginning of interviews.

#### 7.1.3.3. Interviews

Eighteen semi-structured, face-to-face interviews will be conducted with participants receiving the intervention and their carers (paired interviews). Interviews will address feasibility, mechanisms of impact, contextual factors, and acceptability of the intervention. Questions about acceptability and feasibility of research processes such as recruitment, attitudes to randomisation and burden of data collection will also be included. Where face-to-face interviews are not possible, due to Covid restrictions for example, they will be conducted online.

Twenty-four semi-structured telephone or online interviews with professionals across the six study sites will be conducted to examine implementation, feasibility, mechanisms of impact and contextual factors. Questions about experience of training, and the feasibility of research processes will also be included, where practitioners have been involved in these aspects of the study. Interviews will be conducted with four types of professional: geriatricians, physiotherapists, occupational therapists and support workers.

Six clinical research nurses will be interviewed about research processes for MAINTAIN. Interviews will be semi-structured, and conducted online or by telephone. Interviews will explore views on trial recruitment, attitudes to randomisation, reasons for any attrition, feasibility of qualitative and quantitative data collection processes, and research burden on participants.

Interviews will take no longer than around 60 minutes and will be video/audio recorded with participants' permission. If permission is not given, notes will be taken. Participants with dementia and carers will be offered the option to have a break during the interview if required. Encrypted voice recorders will be used to record interviews where conducted face-to-face or by [contact]. Observations

Six non-participant, semi-structured observations of interventions sessions will be conducted to investigate feasibility, implementation and contextual factors affecting the intervention. Sessions will be sampled to include those delivered by physiotherapists, occupational therapists, and research support workers, across different sites.

Four supervision meetings between support workers and either physiotherapists or occupational therapists will be observed, to assess feasibility and implementation factors. Four multidisciplinary team meetings between physiotherapists, occupational therapists and support workers will also be observed to further investigate implementation. These observations will also be non-participant and semi-structured.

Page 33 of 59

Observations of intervention sessions, supervisions and MDTs will take place in person where possible. The study qualitative researcher may record the session using an encrypted voice recorder, and will take notes during and immediately after observations. Where in-person observation is not possible (e.g. due to participant consent for only audio-recording, or Covid restrictions) the recording will be carried out by a practitioner using an encrypted recorder, and sent to the study qualitative researcher via secure file transfer system at the earliest opportunity. The study qualitative researcher will then listen to the recording and take notes. Selected sections of recordings may be transcribed in full for more detailed analysis where necessary.

# 7.1.4. Confirmation of PWD eligibility

The research team will confirm that the PWD is on the primary care QOF dementia register prior to formal recruitment to the study, with the exception of potential participants identified through primary care. Once the potential participant has received the PIS they will be contacted by the clinical researcher via telephone call. During this initial telephone call to discuss participation, the clinical researcher will obtain verbal consent from the PWD to contact their GP practice to check whether the potential participant is on the dementia QOF register. For those referred directly by primary care, we will already know that the participant is on the dementia QOF register.

If the potential participant is on the QOF register, the clinical researcher will contact them again to confirm eligibility and, if the PWD is still interested, to arrange a home visit to take consent and undertake baseline assessment. Potential participants who are not on the dementia QOF register will be sent a letter explaining that they are not eligible by thanking them for their interest.

The clinical researcher will be asked to keep a list of all potential participants who have had contact with the research study team at each stage of the recruitment process. If the potential participant has declined or not responded to a contact from the research team, or if they have not been recruited for any other reason, they will not receive any further contacts from the research team.

#### 7.2. Consent

Informed consent will be required for PWD to participate in the study in accordance with the Declaration of Helsinki. Some participants may lack the capacity give full informed consent due to the nature of dementia. In this case, the provisions of the Mental Capacity Act (2005) will apply. PWD will be asked to give consent appropriate to their level of understanding, this could range from written informed consent to account being taken of verbal and non-verbal communication in determining willingness to participate. The clinical researcher will identify a personal consultee for individuals who lack the capacity to give full informed consent. The personal consultee will be sent a letter explaining the role of a consultee and will be asked for their advice regarding the PWD's participation. If the consultee is not available at the home visit they will instead be contacted by telephone by the clinical researcher to receive their advice about the PWD's participation. If the consultee feels the PWD would not have wanted to participate, the PWD will not be recruited into the study and they will not be contacted any further about the study. If they do not give any opinion it will be assumed that the consent is withheld and the PWD will not be recruited or contacted any further about the study. If a PWD appears distressed by participation or withdrawing consent, they will be excluded from the study without prejudice to clinical care.

Consent will also be sought from all professionals involved in the study to participate in observation and/or interviews and informal discussions. Consent will be required from all professionals involved in

the study. A PIS will be provided to make these expectations clear and describe the rationale for the qualitative aspects of the study.

#### 7.3. Randomisation

Participating services (clusters) will be randomised in a 1:1 ratio to receive either the intervention plus usual care (intervention arm) or continue with usual care services (control arm). Randomisation will be undertaken based on computer-generated random numbers with no stratification factors.

After the baseline assessment, the clinical researcher will inform the central research team. If the participant is in a service (cluster) that is randomised to the intervention arm, the research team will send a referral to the intervention team using a structured referral form with details of the baseline assessments of the PWD and unpaid carer. The intervention team will then arrange an initial intervention assessment within 2 weeks.

# 7.3.1. Method of implementing the randomisation/allocation sequence

In this trial, participating services (clusters) will be randomised prior to recruitment of participants in order to account for the necessary preparation time required for services within the intervention arm. The allocation sequence will be produced by the trial statistician using a random seed and inputted into RedCap Academic. Randomisation of initial sites will then be completed in RedCap Academic, ensuring concealment of the allocation sequence from sites prior to them being randomised. Any sites that act as a replacement for an already randomised site that drops out from the study will be allocated to the treatment group of the site they are replacing. Any additional sites added at a later stage specifically to compensate for slow recruitment of participants, rather than for site drop-out, will be randomised in the same way as initial sites. Allocation concealment will also be ensured for potential participants prior to them consenting to the trial in order to prevent influence on recruitment from participants knowing allocation prior to joining the trial. The research nurses discussing the study with potential participants at each site will not let the participant know which arm the site has been randomised to until after consent has been taken. The participant information sheet will contain information about both arms of the study.

After randomisation is completed a member of the trial team will inform each site of their allocation.

The procedure for replacing sites will be as follows. Any withdrawn sites will be replaced in chronological order with the first site to withdraw being replaced by the first replacement site that has been confirmed as 'ready'. A site will be deemed 'ready' when they have confirmed availability of a therapy team to participate within a study. In the event of no sites needing replacing but where there has been provision to open additional sites, the same procedure will apply as with replacement sites for the order in which they are accepted to randomisation.

Page 35 of 59

### 7.4. **Blinding**

Due to the nature of the intervention and usual care treatment, clinicians and participants involved in the intervention cannot be blinded to treatment allocation. Furthermore, due to the nature of the discussions that patients and clinicians may have during follow-up visits, it is not possible to blind clinicians undertaking data collection to treatment allocation at follow-up. This is because health utilisation data collected at the 3 month time point will likely unblind the clinician to the allocation. As a result, all clinicians involved in this trial will be unblinded throughout.

In order to prevent influence on potential participants joining the trial, participants will be blinded until they are screened and consented but will become unblinded subsequently, as the intervention cannot be delivered as concealed.

Statisticians will be blinded until the completion of the Statistical Analysis Plan in order to prevent bias in proposed analysis or any subgroup analysis sets.

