### 9.2. Statistical analysis

Analyses will be fully pre-specified in a statistical analysis plan that is signed off by the Trial Steering Committee and the Trial Management Group.

Participant flow through the trial will be summarised using a CONSORT flow diagram for cluster randomised controlled trials.

Baseline characteristics of the services and participants will be described using means and standard deviations for continuous variables and numbers and percentages for categorical variables. We will report the following parameters with 95% confidence intervals that are widened to allow for clustering: % of screened people that are eligible; % of eligible people that consent to participate; % of participants that provide data at the 6-month follow-up; and % of intervention arm participants that attend at least 60% of

Page 45 of 59

scheduled sessions. To estimate these parameters, mixed logistic regression models with Satterthwaite's degrees of freedom correction will be fitted to binary outcomes that represent eligibility status, consent status, follow-up status and whether attended at least 60% of the scheduled sessions. The constant from these models will represent the log odds of the parameters which will (along with the 95% CIs) be converted to the percentage scale.

We will also report estimates of the standard deviations for continuous outcomes measured at baseline, 3 months and 6 months.

In order to assess the extent to which randomisation of clusters before recruiting participants may have resulted in recruitment bias due to the research nurses being unblinded, we will report the percentage of eligible people that participate in each of the intervention and control arms and examine the characteristics of the participants between the trial arms.

Finally, in ancillary analyses, we will report intention-to-treat estimates of the effect of the intervention on the continuous outcomes at 3 and 6 months, using 95% confidence intervals to quantify potential effectiveness. The comparison between trial arms will be undertaken by fitting mixed ("multilevel") linear regression models using Satterthwaite's degrees of freedom correction to recognise the small number of clusters in the study. Comparisons will be adjusted for the baseline score of the outcome. No p-values will be reported as it is not an objective of this study to conduct a definitive test of the intervention effect. Analyses will be undertaken using Stata software.

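### A follow-up reason is used to leave recruiters unblinded from screening onward, and the pair may learn its arm before baseline is rated: a partly avoidable risk of bias

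*Protocol*

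**What the plan says.** - **Timing of randomisation.** Protocol 7.3.1 says clusters are "randomised prior to recruitment of participants in order to account for the necessary preparation time required for services within the intervention arm". It then says: "After randomisation is completed a member of the trial team will inform each site of their allocation".
- **Blinding of staff.** Protocol 7.4 explains why data collectors cannot be blinded at follow-up: "This is because health utilisation data collected at the 3 month time point will likely unblind the clinician to the allocation". From this it concludes: "As a result, all clinicians involved in this trial will be unblinded throughout".
- **Who recruits and assesses.** The clinical researcher at each site keeps the screening log (10.1) and contacts the person with dementia "to arrange a home visit to take consent and undertake baseline assessment" (7.1.4).
- **Referral.** After baseline the researcher informs the central team and, for intervention sites, "the research team will send a referral to the intervention team using a structured referral form" (7.3, repeated in 7.6).
- **Concealment from participants.** 7.3.1 and 7.4 keep the arm from participants until they have consented. Neither says that it stays hidden until baseline is finished.
- **Acknowledgement.** Protocol 9.2 and SAP 5.2 accept that early cluster randomisation "may have resulted in recruitment bias due to the research nurses being unblinded". They plan to report participation by arm and to compare participant characteristics. Objective E adds recruitment numbers and loss to follow-up by arm.

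**The concern.** The reason and the rule do not match. Health-utilisation data at 3 months can explain unblinded follow-up. They cannot explain why the person who telephones, consents and assesses a new pair should already know the arm. Preparation time is a reason to tell the therapy service, not the recruiter.

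When clusters are randomised before participants are recruited, a recruiter who knows the arm is a main route to selection bias. Here the same role also administers baseline measures that an assessor can influence. The eligible and consented counts behind the first progression criterion pass through the same staff.

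The participant side has a separate gap. If the arm is disclosed once consent is signed, the rest of that visit may proceed with the carer and the person with dementia aware of it. The DAD, listed as primary in Protocol Table 2, is completed by the carer. Adjusting for the baseline score does not correct a baseline score given with the arm known, and it does not fully remove selection on factors that the score misses.

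**Working it through.** **1. Does the recruiter need the arm?**

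| Task | Where | Arm needed or revealed? |
|---|---|---|
| Screening log | 10.1 | No |
| Consent and baseline at one home visit | 7.1.4, 7.6 | No; the therapist collects GAS, the only arm-specific baseline item |
| Notifying the central team | 7.3, 7.6 | No |
| Referral | 7.3, 7.6; 10.1 | Central in 7.3 and 7.6, but 10.1 lets recruiting Trusts refer where applicable |
| Telling the pair its arm | 7.3.1 | Yes, if the nurse does it |
| Identifying and inviting intervention practitioners | 7.1.3.2 | Yes |
| 12-week HUQ | 9.7, Table 3 | Probably, on the plan's own account |
| Follow-up date (26 or 28 weeks) | 7.7 | Yes, unless issued centrally |

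Nothing from screening to baseline needs the arm. Several other tasks would reveal it unless they were moved.

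**2. How many recruits precede the first 12-week call at a site?** Inputs: 10 per service over 6 months at 1.7 per month (9.1). Assumptions: uniform accrual, and a first recruit between day 0 and month 1.

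- 12 weeks / 4.345 = 2.76 months.
- First recruit on day 0: 2.76/6 = 46% (1.7 × 2.76 = 4.7 of 10.2 per service).
- First recruit at month 1: (1 + 2.76)/6 = 63% of the window has passed. If accrual is instead spread evenly over the remaining 5 months, 2.76/5 = 55%, which lies inside the range.

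Allocation is by site, so if the recruiter makes that call the other 37% to 54% are recruited by someone who probably knows the arm.

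**3. Reproducing the plan's interval for consent.** Inputs: 40% of 150, 6 clusters, ICC 0.05 (9.1).

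- Design effect = 1 + (25 − 1) × 0.05 = 2.2; effective n = 150/2.2 = 68.2.
- Wilson 29.2% to 51.9%; Wald 28.4% to 51.6%. The stated 29% to 51% is reproduced to within about one point.

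**4. What can the by-arm checks exclude?**

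*Consent.* 75 eligible per arm; effective n = 75/2.2 = 34.1.
- SE = √(2 × 0.4 × 0.6 / 34.1) = 0.119.
- Half-width: 1.96 × 0.119 = 23 points; with t on 4 df, 2.776 × 0.119 = 33 points.
- Power (normal approximation) is about 0.13 for 40% v 50% and 0.39 for 30% v 50%.

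*A baseline mean.* 30 per arm; design effect = 1 + 9 × 0.05 = 1.45; effective n = 20.7.
- SE = √(2/20.7) = 0.311 SD.
- Half-width: 0.61 SD (normal) or 0.86 SD (t, 4 df).

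**5. Equal consent does not rule out selection (assumed rates).** Suppose control sites consent 40% of everyone, and intervention sites consent 50% of the fitter half and 30% of the frailer half. Consent is 40% in both arms, but the fitter half makes up 0.50/0.80 = 62.5% of intervention recruits against 50% of controls. The halves of a normal distribution differ by 1.596 SD, so the arms differ by 0.125 × 1.596 = 0.20 SD before baseline adjustment. With 45%/35% the figure is 0.0625 × 1.596 = 0.10 SD; with 55%/25% it is 0.1875 × 1.596 = 0.30 SD. All of these lie well inside the half-widths in step 4.

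**The case against.** A reader might infer that bias is built in, that it is fully avoidable, and that all 60 participants could be protected at no cost. The documents do not support this.

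- **Leakage.** Researchers are embedded in site healthcare teams (7.1.1.2), and nurses help identify intervention practitioners (7.1.3.2). Section 10.1 allows referral through the recruiting Trust. There may be only one nurse at a site (7.1.3.2), and the 12-week HUQ is the clinical researcher's task. One leak unblinds that recruiter for every later recruit. This stands, and it limits what a change can achieve.
- **Limited influence on approach.** Many approaches start from record searches, opt-in forms or letters from other services, and eligibility depends on the dementia register. The recruiter's influence is mainly at the telephone and consent stages. This stands.
- **Baseline measures.** The carer completes the DAD, and the person with dementia completes the EQ-5D-5L and Short-FES-I. Assessor influence is mainly a matter for the Timed Up and Go and the QOL-AD interview. This also stands, but it does not cover a carer who already knows the arm.
- **The risk is studied.** Participants are concealed until consent, the information sheet describes both arms, Objective E addresses concealment, and nurses are interviewed about recruitment. Effect estimates are ancillary, without p-values, and no progression criterion compares arms. This lowers the stakes for the pilot. It does not supply the missing reason, and step 4 shows how little the quantitative checks can exclude.
- **The 0.20 SD.** The rates behind it are chosen so that consent is equal. It shows a mechanism and does not estimate bias in this trial.

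**Conclusion.** The point holds as a risk of bias that is partly avoidable. The reasons in 7.4 cover follow-up only, 7.3.1 informs more people than preparation requires, and the central referral path does not need the recruiter to know the arm. The silence on whether disclosure to the pair waits for baseline is a further gap, and the easiest to close.

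The documents do not show that bias occurred, or how large it would be. What can be sized is the weakness of the checks: about ±23 to ±33 points for consent and ±0.61 to ±0.86 SD for a baseline mean, given the plan's ICC of 0.05 and its target numbers. If the recruiter also makes the 12-week call, later disclosure alone would protect roughly 46% to 63% of recruits, under uniform accrual and a first recruit between day 0 and month 1.

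One limit on currency: the protocol reviewed is version 3.0, while SAP section 6 cites version 5.0, which is not available here. SAP 5.2 still treats the research nurses as unblinded. The SAP's version history places it during follow-up, so recruitment may already have closed.

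**What to change.** 1. In 7.3.1 and 7.4, state that the pair is told its arm only after all baseline measures are completed and recorded.
2. In 7.3.1, send the allocation notice to the therapy service lead, and to the PI if needed. Where the site's set-up allows, do not tell the researchers who screen, consent and take baseline.
3. In 7.4, replace the rule that everyone is unblinded from the start with wording that limits the follow-up reason to follow-up.
4. Route practitioner invitations (7.1.3.2) and any site-level referral (10.1) through someone other than the recruiter. Where a site has two nurses, let the non-recruiting one make the 12-week HUQ call, and align 9.7 and Table 3.
5. Record when and how a recruiter learns the arm, and report it under Objective E.

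The cost is protocol wording, a narrower allocation notice, some reassignment of tasks and one extra log item. Items 1 and 2 are nearly free. Protection stays partial: one-nurse sites have no second person for the call, and leakage within embedded teams is likely. If recruitment has closed, items 1 to 5 should go into the design of the definitive trial, and the pilot report should say that recruiters knew the arm and whether pairs could have known it at baseline.
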